4. LIST OF ABBREVIATIONS AND DEFINITIONS OF TERMS

Table 2: Abbreviations and Definitions of Terms

Abbreviation	Definition
AE	adverse event
A _y	cornering speed threshold exceeded
BAC	blood alcohol concentration
BMI	body mass index
CBD	Cannabidiol
CNS	central nervous system
CPT	continuous performance test
CRCDS2	Cognitive Research Corporation Driving Simulator
C-SSRS	Columbia Suicide Severity Rating Scale
DIDS	Drug Impaired Driving Scenario
DAT	Divided Attention Test
DTT	Dual Task Test
EC	ethics committee
ECG	Electrocardiogram
eCRF	electronic case report form
ET	early termination
FAS	Full Analysis Set
FDA	Food and Drug Administration
GABA _A	γ aminobutyric acid-gated chloride channel
GCP	Good Clinical Practice
HIV	human immunodeficiency virus
ICF	informed consent form
ICH	International Council for Harmonisation of Technical Requirements for Pharmaceuticals for Human Use
KSS	Karolinska Sleepiness Scale

Abbreviation	Definition
MTS	Matching To Sample
MMRM	mixed model for repeated measures
NADS	National Advanced Driving Simulator
NHTSA	National Highway Transportation Safety Administration
PFN	Pathfinder Number
PD	Pharmacodynamics
PK	Pharmacokinetic
PO	by mouth
QA	quality assurance
QC	quality control
QTcF	QT corrected according to Fridericia's formula
qAM	each morning
SAE	serious adverse event
SDC	Symbol Digit Coding
SAT	Shifting Attention Test
SDLP	Standard Deviation of Lateral Position
SOC	system organ class
SOP	Standard Operating Procedure
SS	Safety Set
SUSAR	suspected unexpected serious adverse reaction
TEAE	treatment-emergent adverse event
TOVA	Test of Variables of Attention
THC	Tetrahydrocannabinol
WHO	World Health Organization
VAS	visual analog scale
VSC	Visual Sequence Comparison

5. INTRODUCTION

Following recommendations from the National Transportation Safety Board (NTSB) that the U.S. Department of Transportation (DOT) establish a list of approved medications and classes of medications that may be used safely when operating a vehicle (NTSB, 2000 as cited in Kay and Loga, 2011) the National Highway Traffic Safety Administration (NHTSA) released its *Drugs and Human Performance Fact Sheets* (Cooper & Logan, 2004, as cited in Kay and Logan 2011) representing the current scientific knowledge in the area of drugs and human performance for 16 substances. However, studies determining effects on performance and on driving reflect myriad study methodologies. Similar efforts by the National Institute on Drug Abuse (NIDA, 2007 as cited in Kay and Logan, 2011) and by the European Union to produce lists characterizing the impairing effects of drugs yielded similarly fraught issues regarding the inability to generalize results secondary to methodological differences across studies. Subsequently, NHTSA convened an expert panel in 2008 and 2009 (Kay and Logan, 2011) with the goal of determining whether a list of drugs could be developed indicating which drugs or classes of drugs may pose a risk to driving.

Kay and Logan (2011) reported that the panel agreed that a limited number of drugs generally pose a low risk to driving when taken according to approved prescribing information under appropriate medical oversight. However, the panel also recognized that even among drugs generally considered safe for driving, adverse reactions and interactions may occur that could impair driving performance. The panel was of the opinion that some specific drugs and drug classes are clearly impairing, including sedatives, hypnotics, sedating antihistamines, narcotic analgesics, hallucinogens, antipsychotics, and muscle relaxants, even at therapeutic or sub-therapeutic doses. Furthermore, the panel noted that a potent barrier to categorizing drugs with respect to driving impairment risk is “lack of a common, standardized protocol for assessing the impairing potential of drugs,” (Kay and Logan, 2011, p. 7). That is, there is recognition of the need for a structured, standardized protocol to assess the driving impairment risk of drugs, as current systematic reviews reveal inconsistencies in methodology, failures to address inconsistencies relative to dosing, time since dosing, subject characteristics and pattern of use, and the use of non-standardized testing methodologies.

As a result, a tiered assessment protocol was proposed, including the following tiers: I) pharmacology/toxicology review to identify drugs likely to impair driving; II) epidemiological review to identify the relative risk of impairment for drugs/drug classes based on comparison to control populations or by culpability assessment; and III) standard behavioral assessment (Kay and Logan, 2011). Tiers I and II identify the drugs most likely to impair driving, leading to the activation of Tier III. The current study is designed as a structured, standardized approach based on the Essential Driving Ability Domains (EDAD) Model described in Kay and Logan (2011) in order to validate a standardized protocol to evaluate drug impaired driving.

Bulk cannabis was chosen as the study drug given its known chemical properties and range of cannabis THC concentrations. This source of cannabis has been used for a series of NHTSA and NIDA sponsored driving studies conducted at NADS (Brown et al., 2019; Brown et al., 2020; Hartman, Anizan, Jang, Brown, Yun...Huestis, 2015; Hartman et al., 2015a; Hartman et al., 2015b; Hartman et al., 2016; Hartman, Brown, Milavetz, Spurgin, Pierce...Huestis, 2015;

Hartman, Jang, Spurgin, Yun, Gorelick...Huestis, February 2015; Miller et al., 2020; Smith et al., November 2018).

5.1. Study Rationale

SELECTION OF CANNABIS FOR VALIDATION OF ASSESSMENT METHODOLOGY: As the legal atmosphere surrounding cannabis use continues to evolve, the potential for increased usage among drivers raises questions regarding its effects on driving ability. Epidemiological studies have examined the relationship between cannabis use and motor vehicle crash risk, injury risk, and fatal crash risk. Cannabis tends to be the most common illicit substance present in injured drivers (Legrand et al., 2013; Brubacher et al., 2016) and the second only to alcohol as the most common recreational substance among injured drivers (*ibid*). While the presence of cannabis in injured drivers in Italy occurred to a lesser extent than did the presence of cocaine and benzodiazepines (Siliquini et al., 2007), another study found individuals aged 35 – 54 years who reported using cannabis within the past year had significantly greater odds of reporting having been in a motor vehicle collision (Mann et al., 2010). Cannabis use has been shown to be associated with self-reported instances of road rage, driving mistakes, and accident risk in Pakistani truck drivers (Mir et al., 2012).

Methodological and design differences and limitations notwithstanding, the majority of case-controlled studies show an increase in motor vehicle crashes (MVC) for drivers under the influence of cannabis (DeBalzoa et al., 2018; Kuypers et al., 2012; Jamt et al., 2018; Li et al., 2013; Baldock & Lindsay, 2015; Chihuri & Chen, 2017). Of two case-controlled studies that did not find an increase in crash risk, one found an association between cannabis use and unsafe driving (Dubois et al., 2015) while the other study reported inconclusive results for the effect of cannabis when used in isolation (Steinemann et al., 2018). DeBalzoa et al. (2018) found a high degree of association between cannabis use and collisions resulting in driver injuries yet concluded that risk of serious injury and fatal injury for individuals testing positive for cannabis alone was relatively low. Contradictory findings have been reported for the role of cannabis (alone) in fatal crashes (Gjerde et al., 2011; Chihuri & Chen, 2017; Martin et al., 2017).

Experimental research investigating the effects of cannabis on driving have been conducted with over-the-road and simulated driving tests. There has been little consistency in the methodology applied across researchers and generally a lack of replication. Investigators have studied drivers with markedly different characteristics which likely interact with the effect of the drug (e.g., patterns of substance use, prior driving experience, and age). Published studies also show a wide range of doses and delivery systems and generally fail to show an association between exposure and serum THC. Furthermore, driving simulator studies have not been conducted using anything approaching a standard set of driving challenges or tasks.

In spite of these methodological issues, there is general agreement that cannabis increases weaving. However, the relationship between cannabis exposure and magnitude of weaving remains to be determined. The impact of cannabis on lane crossings has been inconsistent. Cannabis (without concomitant alcohol consumption) generally results in slower driving speeds and greater headway distances in nighttime conditions. With respect to neurocognitive testing, cannabis has consistently been shown to impact performance under multitasking conditions.

SELECTION OF ALPRAZOLAM FOR USE AS ACTIVE COMPARATOR: Alprazolam is the most frequently prescribed benzodiazepine for treating panic disorder and anxiety disorders (RxList, 2005 as cited in Leufkens et al., 2007). The cognitive and psychomotor effects of alprazolam have been well-documented in older studies (Verster and Volker, 2004b as cited in Leufkens et al., 2007; Bertz et al., 1997 as cited in Leufkens et al., 2007; Ellinwood et al., 1985 as cited in Leukens et al., 2007; Greenblatt et al., 1988 as cited in Leufkens et al., 2007; Kroboth et al., 1998 as cited in Leufkens et al., 2007; Rickels, 2004 as cited in Leufkens et al., 2007; Scavone et al., 1992 as cited in Leufkens et al., 2007; Smith et al., 1984 as cited in Leufkens et al., 2007; Subhan et al., 1986 as cited in Leufkens et al., 2007; Vermeeren et al., 1995 as cited in Leufkens et al., 2007; Verster et al., 2002 as cited in Leufkens et al., 2007). While limited in number, results from the more recent studies available reveal that alprazolam has an adverse impact on driving performance. The most consistent findings are increased weaving (Leufkens et al., 2007; Stone et al., 2015; Brown et al., 2018; CRC data on file 2019 and 2020; Verster et al., 2002), increased lane departures (Sone et al., 2015; Brown et al., 2018; CRC data on file 2019 and 2020; Pearlman et al., 2020; Verster et al., 2002), and poor speed maintenance (Brown et al., 2018; Pearlman et al., 2020; CRC data on file 2017, 2019, and 2020; Verster et al., 2002). Additional safety endpoints show increased collision risk and failure to adjust speed in corners (CRC data on file 2017, 2019, 2020; Verster et al., 2002).

With regards to neurocognitive functioning, alprazolam has been shown to impair immediate and delayed recall of word lists (Leufkens et al., 2007; Reissig et al., 2014; Hindmarch et al., 2005; Snyder et al., 2005), impair tracking ability (Hindmarch et al., 2005; Leufkens et al., 2007; Verster et al., 2002), slow reaction times (Leufkens et al., 2007; Stone et al., 2015; Reissig et al., 2014; Hindmarch et al., 2005; CRC data on file 2017, 2019, 2020), and adversely affect information processing speed (Reissig et al., 2014; Hindmarch et al., 2005; CRC data on file 2017 and 2019; Pearlman et al., 2020).

PURPOSE OF PRESENT STUDY: The primary purpose of the current study is to establish a standardized protocol for assessing drug impaired driving. Validation of this methodology is to be accomplished with a study using cannabis, alprazolam, and matching placebo. As part of this research effort, investigators have worked to identify the driving tasks and cognitive abilities found to be most vulnerable to the impairing effects of cannabis. In addition, an effort was made to identify the subject characteristics associated with increased vulnerability to the impairing effects of cannabis. Worked was conducted to develop a methodology for determining when drivers are safe to resume driving after drug exposure. The current study is designed to test these hypotheses.

Simulated driving will be performed using an updated version of Cognitive Research Corporation's Driving Simulator (CRCDS2 MiniSim). The prior version of this simulator has been used in dozens of driving studies submitted for regulatory review. Driving performance will be assessed using an approximate 1-hour Drug Impaired Driving Scenario (DIDS), comprised of suburban, urban and highway driving tasks. The scenarios include challenges designed to assess lane position control, speed control, safety awareness and responsivity, driving-related decision making, multitasking, and vigilance. These domains correspond to the Essential Driving Ability

Domains described by Kay and Logan (2011). In addition, cognitive functions associated with driving performance and self-report measures will also be administered.

Consistent with the principles outlined in the FDA Guidance for Industry (2017), this study includes both a positive (active) and placebo control condition. The study is designed to assess the duration of drug effects. Readiness to resume driving will be assessed using both self-report and objective testing. Subjects will include regular (daily) users and weekly users of cannabis. The intent is to assess the impact of pattern of drug use on driving performance. A cross-over study design will be utilized to maximize statistical power.

Cannabis will be administered once in the morning on Day 2. Effects on driving and cognition will be assessed from 30 to 45 minutes after dosing. Cognitive and self-report measures will be repeated approximately 3.5 hours post-dose to assess residual effect. There will be a one-week washout between treatment periods. Subjects will be instructed to refrain from drug use for 7 days prior to treatment period 1 and to continue to abstain from (non-study) drug use for the duration of the trial.

Alprazolam was selected as the active comparator and to further validate the CRCDs-2 and the DIDS scenario. The negative effect of Alprazolam on driving performance has been demonstrated in both on-the-road and simulated driving studies (Pearlman et al., 2019; CRC, data on file; Leufkens 2009; Leufkens & Vermeeren 2014; Mets 2011; Simen 2015; Verster 2011). Additionally, as alprazolam is the most commonly prescribed psychotropic in the U.S., use of the drug remains a concern for traffic safety.

5.2. Dose Rationale

One dose of cannabis will be evaluated in this study:

- Bulk cannabis (6.18% THC/ <0.025% CBD) in a 500mg dose providing 30.9 mg THC administered by inhalation via vaporization on Day 2 in each of 3 treatment periods

This dose was selected based on comparability of THC concentrations with a currently in development medicinal cannabis medication, PPP001 (*Tetra Bio-Pharma Inc*), that provides 26.6 mg THC. Prior research conducted by the research team also demonstrates tolerability of THC concentrations of this level (6-7% THC in a 500mg vaporized dose).

The active comparator, alprazolam, will be administered at a dose of 0.75 on Day 2, based on previous demonstration of impaired performance on the driving simulator test following administration of a single oral dose at this level (CRC, data on file).

6. STUDY OBJECTIVES AND ENDPOINTS

6.1. Study Objective

The primary objective of this study is to validate the DIDS scenarios using the CRCDS-2 driving simulator, by assessing the acute effects of cannabis relative to placebo on simulated driving performance. Assay sensitivity will be demonstrated by the significant effect of alprazolam 0.75 mg on driving and cognitive endpoints. A secondary objective of the study is to assess the effects of cannabis on cognitive and psychomotor functioning relative to placebo. Another objective of this study is to evaluate the potential relationship between THC blood concentration and driving performance endpoints.

6.2. Endpoints

6.2.1. Key Endpoints

A key driving performance endpoint is Standard Deviation of Lateral Position (SDLP) after a single dose of cannabis.

6.2.2. Other Key Endpoints

- Driving Performance Endpoints
 - Lane exceedance; including number, maximum duration, and area of exceedance
 - Excessive speed count
 - Average speed and speed deviation
 - Excessive Ay (cornering speed threshold exceeded) and Total Crashes
 - Divided Attention: Correct Responses, Omission Errors, Commission Errors, Reaction Time, Standard Deviation of Reaction Time
 - Traffic light violations
 - Gap decision making performance
 - Response to Crash Likely Events
 - Attention to mirrors task
 - Working memory task
 - Coherence
- CogScreen Symbol Digit Coding Test
 - Number of correct responses
 - Response Accuracy
 - Standard deviation of reaction time
- CogScreen Symbol Digit Coding – Immediate Recall
 - Immediate recall accuracy
- CogScreen Symbol Digit Coding – Delayed Recall
 - Delayed recall accuracy
- CogScreen Visual Sequence Comparison Test

- Response speed
- Response accuracy
- Standard deviation of reaction time
- CogScreen Divided Attention Test
 - Response speed
 - Number of premature responses
 - Response accuracy
 - Lapses
 - Multitasking scores
- CogScreen Matching To Sample Test
 - Response speed
 - Response accuracy
 - Standard deviation of reaction time
- CogScreen Pathfinder Number
 - Response speed
 - Response accuracy
 - Response coordination
- CogScreen Shifting Attention Test
 - Response speed
 - Response accuracy
 - Standard deviation of reaction time
- CogScreen Dual Task Test
 - Tracking error
 - Number of boundary hits
 - Previous Number response speed
 - Previous Number response accuracy
 - Previous Number standard deviation of reaction time
 - Multitasking scores
- Test of Variables of Attention (TOVA)
 - Response time variability (by quarter & overall)
 - Response speed (by quarter & overall)
 - Commission errors (by quarter & overall)
 - Omission errors (by quarter & overall)
- Self-reported readiness to drive (“Right now do you feel safe to drive?” [Yes/No])
- VAS to assess participant’s motivation and self-appraisal of their driving performance
- Other self-report measures

6.2.3. Additional Endpoint(s)

Other endpoints of this study are:

- Changes from baseline in vital signs, clinical laboratory data, ECG parameters, and suicidal ideation and behavior using the Columbia Suicide Severity Rating Scale (C-SSRS)
- Relationship between blood concentration of THC and SDLP or other driving or cognition endpoints

7. INVESTIGATIONAL PLAN

7.1. Overall Study Design

This is a randomized, double-blind, active- and placebo-controlled, 3-arm, 3-period crossover study to assess the effects of cannabis on simulated driving performance and related cognitive functions in healthy male and female adult cannabis users. The study design is provided in Figure 1. The schedule of assessments is provided in [Table 1](#).

Following a screening/training period of up to 14 days, eligible participants will be admitted to NADS on Day 1 of Period 1. Baseline performance for cognitive testing will be obtained and subjects will practice the CRCDS2-MiniSim driving simulator. Participants will be randomized 1:1:1 into one of 6 treatment sequences as shown in Table 4. Study drug will be administered by inhalation on Day 2 with the alprazolam dosing approximately 40 minutes prior to the cannabis dosing (the first cannabis dose will occur at approximately 8:40); precise timing is relative, as subject dosing will be staggered/offset to accommodate staffing and subject flow. Blood samples for pharmacokinetic analysis will be drawn pre-dose and again 40 minutes post-dose and 3.25 hours post-dose. Symbol Digit Coding (SDC), Pathfinder Number (PFN), Readiness to Drive Question, and the Karolinska Sleepiness Scale (KSS) will be administered approximately 30 minutes post-dose. A baseline KSS will also be administered prior to dosing. Driving assessments will begin approximately 45 minutes following dosing. Driving performance will be assessed via the approximate 1-hour Drug Impaired Driving Scenario (DIDS), on the CRCDS2-MiniSim driving simulator, comprised of suburban, urban and highway driving tasks. The scenario includes challenges designed to assess lane position control, speed control, safety awareness and responsivity, driving-related decision making, multitasking, and vigilance. Immediately after completing the driving simulation, subjects will be administered the visual analog scales, or VAS, followed by the cognitive test battery (SDC, Visual Sequence Comparison [VSC], Divided Attention Test – Dual [DAT-Dual], PFN, SDC Delayed Recall [SDCDR], Shifting Attention Test – Instruction [SAT-Instruction], MTS, Dual Task Test – Combined [DAT – Combined], and TOVA). At approximately 3.5 hours post-dose the cognitive test battery (i.e., SDC, VSC, DAT-Dual, PFN, SDCCDR, SAT – Instruction, MTS, DTT – Combined, TOVA) and self-report measures will be repeated.

Subjects will undergo initial driving simulator training and practice during the Screening period and will complete a practice drive on Day 1 of each treatment period.

Subjects will be discharged from NADS on the afternoon of Day 2 of each treatment period approximately 5.33 hours post-dose, provided they are medically stable for discharge in the opinion of the Investigator. The subject will not be able to drive themselves home and will have transportation arranged.

After a washout of at least 7 days, but no more than 10 days, between administration of the last dose in one period and administration of the first dose in the next period, subjects will be readmitted to NADS on Day 1 of Period 2 and receive study drug according to the assigned

treatment schedule. All study assessments will remain the same as in Period 1. The same process will be repeated for Period 3.

Seven days (± 2 days) after discharge from Period 3, subjects will receive a follow-up/end-of-study phone call from the site to evaluate the presence of any AEs and collect any new concomitant medication/procedure information.

The schedule of assessments is provided in [Table 1](#). The following regimens will be assessed:

- Cannabis (inhaled) on Day 2
- Alprazolam 0.75mg on Day 2
- Placebo on Day 2

Subjects will receive 0.75mg of alprazolam (over-encapsulated) or matching placebo capsule 40 minutes prior to administration of inhaled cannabis or matching placebo inhalation/vaporizer on Day 2 of each Treatment Period. Matched placebo tablets and/or vaporizers will be administered as necessary to maintain the blind across the 3 treatment regimens.

7.2. Number of Subjects

Approximately 12 subjects will be randomized and dosed. Efforts will be made to randomize an approximately equal number of male and female subjects. Efforts will be made to randomize an approximately equal number of “low frequency users” (i.e., 1 – 10 uses of cannabis per month) and “high frequency users” (i.e., > 20 uses of cannabis per month).

7.3. Treatment Assignment

Subjects will be randomized into one of 6 treatment sequences (Table 3).

Table 3: Treatment Sequences

Sequence	Treatment Period		
	1	2	3
1	A	B	C
2	B	C	A
3	C	A	B
4	A	C	B
5	B	A	C
6	C	B	A

Treatment A: Cannabis on Day 2

Treatment B: Alprazolam 0.75mg on Day 2

Treatment C: Placebo on Day 2

Note: Matched placebo capsule or vaporizers will be administered as necessary to maintain the blind across the 3 treatments.

7.4. Criteria for Study Termination

NHTSA may terminate this study or any portion of the study at any time for safety reasons including the occurrence of AEs or other findings suggesting unacceptable risk to subjects, or for administrative reasons. In the event of study termination, NHTSA will provide written notification to the Investigator. The investigational site must promptly notify its ethics committee and initiate withdrawal procedures for subjects.

8. SELECTION AND WITHDRAWAL OF SUBJECTS

8.1. Subject Inclusion Criteria

Qualified subjects will meet all of the following criteria:

1. Subject understands and provides written informed consent prior to the initiation of any protocol-specific procedures.
2. Subject is able to comprehend and willing to comply with the requirements of the protocol.
3. Subject is a healthy male or female adult, 19 to 45 years of age, inclusive, at Screening.
4. Subject has a regular sleep pattern (usual bedtime between 21:00 and 00:00).
5. Subject has Score <10 on Epworth Sleepiness Scale at Screening.
6. Subject is able to reliably perform study assessments at Screening (On practice drive, SDLP no higher than 1 standard deviation greater than the mean for normal healthy adults completing the practice scenario; subject exhibits ≥ 11 instances of lane exceedance; or subject has fewer than 7 correct hits on the Divided Attention task; CogScreen SDC Correct no less than 1 standard deviation below the mean for healthy adults); demonstrates the ability to understand task instructions at Screening; and is physically (e.g., adequate manual dexterity, vision, and hearing) and cognitively capable of performing study tasks at Screening.
7. Subject possesses (and is willing to provide) a valid driver's license and is an active driver (minimum of approximately 3,000 miles per year for the previous 3 years).
8. Subject is determined to be (by self-report) either an infrequent user of cannabis (i.e., 1-10 uses per month) or a frequent user of cannabis (i.e., >20 uses per month) over the preceding 90 days.
9. Subject is willing to abstain from cannabis use (other than study drug) beginning 7 days prior to admission for the first treatment period (Day 1) until discharge from the facility on Day 2 of period 3.
10. Female subjects must meet one of the following criteria: 1) If of childbearing potential, female subjects agree to use two contraceptive regimens or remain abstinent during the study; or 2) if of non-childbearing potential, female subjects should be surgically sterile or in a menopausal state.

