8.2. Subject Exclusion Criteria

Subjects who meet any of the following criteria are disqualified from participation in this study:

1. Subject has a significant history and/or presence of hepatic, renal, cardiovascular, pulmonary, neurological, psychiatric, gastrointestinal, hematological, immunologic,

ophthalmologic, metabolic, or oncological disease, or any other medical issue that would, in the opinion of the Investigator, present undue risk for the subject in the study.

2. Subject has a history of suicidal behavior within 24 months of Screening, has answered YES to questions 3, 4, or 5 on the C-SSRS at Screening or at any clinic admission, or is currently at risk of suicide in the opinion of an Investigator.
3. Subject has a recent history (within 6 months prior to Screening) of substance use disorder (including alcohol) (as judged by the Investigator) or regularly consumes >2 alcoholic drinks/day during the last 3 months prior to Screening (1 alcoholic drink is approximately equivalent to: beer [284 mL], wine [125 mL/4 ounces], or distilled spirits [25 mL/1 ounce]). Subjects who consume 3 drinks per day but less than 14 drinks per week may be enrolled at the discretion of the Investigator.
4. Subject demonstrates simulator sickness questionnaire scores which are indicative of simulator sickness as defined in the driving simulation operations manual.
5. Subject regularly consumes excessive amounts of caffeine, defined as greater than 6 servings of coffee, tea, cola, or other caffeinated beverages per day.
6. Subject smokes more than 10 cigarettes or e-cigarettes, or 3 cigars or pipes per day, or is unable to refrain from smoking during study visits.
7. Subject has been exposed to an investigational drug or device within the 30 days, or 5 half-lives (if known), whichever is longer, prior to Screening.
8. Subject has used a prescription or over-the-counter medication known to cause sedation within 7 days prior to Admission for Period 1 and is unwilling or unable to refrain from sedating medication use during study participation.
9. Subject has used any benzodiazepine, barbiturate, or GABA_A modulator (e.g., eszopiclone, zopiclone, zaleplon, and zolpidem) within 28 days prior to Admission for Period 1 or is unwilling or unable to refrain from medication use during study participation.
10. Subject has a history of hepatitis B surface antigen, hepatitis C antibodies, or human immunodeficiency virus (HIV) antibodies 1 or 2.

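### Inclusion criterion 6 states two of its four performance limits the wrong way round, so as written it admits subjects with 11 or more lane exceedances or fewer than 7 divided-attention hits

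*Combined protocol and SAP*

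**What the plan says.** Protocol section 8.1 opens its list with the rule "Qualified subjects will meet all of the following criteria". Criterion 6 then begins "Subject is able to reliably perform study assessments at Screening" and gives four performance limits in a parenthesis:

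- practice-drive SDLP: "SDLP no higher than 1 standard deviation greater than the mean for normal healthy adults completing the practice scenario";
- lane exceedance and divided attention, joined by 'or': "subject exhibits ≥ 11 instances of lane exceedance; or subject has fewer than 7 correct hits on the Divided Attention task";
- symbol digit coding: "CogScreen SDC Correct no less than 1 standard deviation below the mean for healthy adults".

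After the parenthesis, the criterion also asks that the subject understand the task instructions and be physically and cognitively capable of the tasks. These clauses carry no numeric limit. Criterion 6 in the Synopsis has the same wording.

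The exclusion list in section 8.2 works the other way: "Subjects who meet any of the following criteria are disqualified from participation in this study". Its only simulator-related item concerns simulator sickness. It sets no limit on lane exceedance or divided attention.

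**The concern.** Fail conditions joined by 'or' suit an exclusion list, where meeting any one item disqualifies. Here they stand in an inclusion list, beside two limits written as passes. Taken literally, the criterion counts poor performance on two tasks as evidence that a subject performs reliably.

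The two measures are also outcomes. Section 6.2.2 lists "Lane exceedance; including number, maximum duration, and area of exceedance" and "Divided Attention: Correct Responses, Omission Errors, Commission Errors, Reaction Time, Standard Deviation of Reaction Time" among the Other Key Endpoints. The Synopsis aims for 6 to 8 completers, so one wrongly admitted completer would be 1/8 = 12.5% to 1/6 = 16.7% of them. Section 13.1 defines no per-protocol set. A wrongly admitted subject who is treated and has an SDLP value therefore stays in the Full Analysis Set used for the primary analysis.

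**Working it through.** The plan gives no figure to reproduce, so the check is one of wording and logic.

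**Direction of each limit (section 8.1, criterion 6)**

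| Measure | Limit as written | Form |
|---|---|---|
| SDLP | at or below mean + 1 SD | pass |
| Lane exceedances (LE) | 11 or more | fail |
| Divided Attention hits (DA) | fewer than 7 | fail |
| SDC Correct | at or above mean − 1 SD | pass |

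Two of the four limits are passes and two are fails.

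**Which results the text admits.** Score each measure good or poor, giving 2⁴ = 16 profiles. The criterion's purpose fits one of them, all four good. The semicolons and the single 'or' in mid-list do not settle how the items combine, so four readings were counted.

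1. *'Or' joins only the two middle items:* SDLP good AND (LE poor OR DA poor) AND SDC good. SDLP and SDC are fixed. Of the 2 × 2 = 4 combinations of LE and DA, all but good/good qualify: 4 − 1 = 3 profiles. The all-good profile is refused.
2. *'Or' spans the three driving items:* (SDLP good OR LE poor OR DA poor) AND SDC good. SDC is fixed. Of the 2³ = 8 combinations of the other three, only SDLP poor with LE and DA good is refused: 8 − 1 = 7 profiles. One is the all-good profile. The other 7 − 1 = 6 have LE or DA poor, and 3 of those 6 also fail the SDLP limit.
3. *All items joined by 'and':* SDLP good, LE poor, DA poor, SDC good: 1 profile. The all-good profile is refused.
4. *'Or' across all four items:* everything except SDLP poor, LE good, DA good, SDC poor: 16 − 1 = 15 profiles.

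| Reading | Profiles admitted (of 16) | All-good admitted? | Admits poor LE or DA? |
|---|---|---|---|
| 1 | 3 | no | yes, all 3 |
| 2 | 7 | yes | yes, 6 of 7 |
| 3 | 1 | no | yes, the only one |
| 4 | 15 | yes | yes |

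Readings 1 and 2 are the most natural. All four admit subjects with 11 or more exceedances or fewer than 7 hits, and none reproduces the stated purpose.

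**Is it corrected elsewhere?** The Synopsis repeats the wording. Section 8.2 has no matching exclusion. Section 11.1.1 refers to an operations manual for scenario detail. That manual is not among the documents, and nothing in them says that it restates or overrides criterion 6.

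**The case against.** The strongest reply is that nobody would apply the text literally. The opening words of criterion 6 show that the two limits are reasons to fail, and a site that required poor driving for entry would notice. The clauses after the parenthesis also give the investigator some protection, because a poor score alone does not qualify a subject. The trial is a three-period crossover with a random subject effect (sections 7.1 and 13.5), so each subject is compared with their own placebo period. Poor lane-keeping at entry would not by itself bias the cannabis-placebo contrast. The limit on SDLP, the key endpoint, is in the right direction and is bypassed only if the 'or' reaches it. Finally, counting profiles says nothing about how many subjects are affected.

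Much of this stands as a limit on the consequences. Misapplication is a risk that the documents do not show to have occurred, and the profile counts describe the logic rather than the size of any harm. None of it makes the text correct. The remaining clauses set no number. A site that follows the evident purpose departs from the written criterion, and a monitor has no correct text to check against. Someone who mentally reverses the two limits must still guess whether failing one of them is enough to disqualify.

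**Conclusion.** The concern holds. Two of the four limits in criterion 6 are inverted in both places where the criterion appears, and nothing in the documents corrects them. Across the four readings the text admits 1, 3, 7 or 15 of the 16 profiles, always including poor performers on lane exceedance or divided attention. Two of the four readings refuse the subject the criterion sets out to describe.

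The intended direction is inferred from the stated purpose and the two adjacent limits; the sponsor has to confirm it. The effect on the trial's results cannot be quantified, and the documents do not show which direction the site applied. The wording still needs correcting because this is an operative entry threshold in a very small trial.

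**What to change.** In section 8.1 and in the Synopsis, restate the parenthesis of criterion 6 as pass conditions joined by 'and', keeping the sponsor's cut-offs:

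- on the practice drive, SDLP no more than 1 SD above the healthy-adult mean;
- and fewer than 11 lane exceedances;
- and at least 7 correct Divided Attention hits;
- and CogScreen SDC Correct no more than 1 SD below the healthy-adult mean.

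The sponsor should confirm that this direction and the 'and' logic are intended and agree with the operations manual. For any subject already screened, the site should record which direction was applied.

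The cost is one sentence changed in two places and a check of the screening records. If the site already screens in the inferred direction, conduct does not change.
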